
Scale- Conflict Tactics Scale - Gender Minority Stress Risk and Resilience Scale - Post Traumatic Stress Disorder Symptom Checklist for DSM-5 (PCL-5)- Sexual Assertiveness Questionnaire- Resistance Tactics Survey- Dating Self-Protection - Illinois Rape Myth Acceptance - Resistance Self-Efficacy - Personal Progress- Transgender Congruence Scale - Depression Anxiety and Stress Scale - Quick Drinking Screen - DAST-10Brief acceptability checklists will be administered after each course session, which will contain a brief list of topics covered during that training session and participants will indicate which of the topics they felt were adequately covered (See page 38 of Assessment Packet, "Satisfaction and Fidelity Forms" for example items and formatting of this checklist). Lastly, an exit interview will be scheduled on the final day of the course, and will take place over the weeks immediately following the completion of the course. Interviews will be video recorded using the Zoom videoconferencing platform. The video-recorded qualitative interviews will be recorded and transcribed verbatim using the Zoom transcription function (omitting identifying information) and verified for accuracy. We will use three strategies to improve retention, based on an intensive evidence-based follow-up protocol with which the PI has considerable experience. First, participants will be compensated for completion of the assessment appointments at increasing increments over time (i.e., \$40 for baseline, \$30 for follow-up immediately after the course and \$30 for the exit interview after the course, \$80 for 6-month follow-up). Second, at baseline, participants will be asked to provide extensive locating information and to provide names of two local persons to be contacted in the event that the participant cannot be reached. This information will be updated at the time of follow-up survey administration. Third, participants will receive \$10 cash for each of the five session acceptability checklists they complete (one per session attended- up to \$50 total) which will be distributed at session 3/5 (up to \$30) and 5/5 (up to \$20). Analyses will be of two primary types: (a) examinations of whether feasibility targets were met across a variety of measures; and (b) examinations of the efficacy of the tailored ESD violence prevention intervention. We will use repeated measures one-way ANOVA to test if the tailored ESD curriculum has statistically significant effect on measures of behavioral and psychological/attitudinal change. If a significant effect is detected, we will use Tukey's pairwise-comparison procedure to compare all treatment means, with a 95% family confidence coefficient. To assess changes in exposure to victimization, we will collapse into three levels: (a) no history of victimization; (b) moderate victimization; (c) severe victimization. For this categorical data, a chi-square test of independence will be performed to compare posttreatment vs. pre-treatment, and 6-month FU vs. pre-treatment respectively to assess the preliminary efficacy of the program, with a family-wise type I error controlled at 0.05 using Bonferroni procedure. Our efficacy outcomes are exploratory and powered to detect large effect sizes. In the largest scale RCT of an ESD violence prevention program to date, rates of completed assault among women receiving resistance training were reduced by half at 1-year follow-up. However, as there are no existing studies that report on ESD efficacy among TW, we will use results of our exploratory efficacy analysis to shape power analyses for a subsequent, fully powered, RCT

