**Initial Application** 

**[name]** 

## 6. Research Design - Procedures and Risks

Participant Group	
List all research related procedures/data collection methods involving interaction or intervention with participants; use the Add New Procedure and Risk button to add each method.	List all research related procedures/data collection methods involving interaction or intervention with participants; use the Add New Procedure and Risk button to add each method.
Procedure	Self-Report Questionnaires
Where it will take place?	Self-report questionnaires will be administered virtually. Participants will have the option to complete baseline and course follow-up surveys remotely at home, or using iPads or their phones at God's Love We Deliver before and after the course.
When it will take place?	Self-report questionnaires will be administered to each participant 3 times; baseline (before the ESD intervention), follow-up directly after the intervention, and 6-month follow-up.
Frequency	Self-report questionnaires will be administered to each participant 3 times; baseline, follow-up immediately following course completion, and 6-month follow-up.
Is procedure optional for participants?	Yes
Associated risk or discomfort	Questionnaires include some questions concerning personal or emotional matters that could cause mild, temporary psychological discomfort.
Anticipated severity of risk or discomfort	No more than minimal risk
Expected frequency of risk or discomfort	Self-report questionnaires will be administered to each participant 3 times; baseline, follow-up immediately following course completion, and 6-month follow-up.
Risk reduction or mitigation method	While every possible step will be taken to minimize such risk, if participants have any concerns about any aspect of the study, consent documentation will make it clear that they may refuse to continue with the study at any time, without penalty. In addition, we will remind participants during the course of all assessments that they do not have to respond to any questions they do not wish to and may discontinue participation at any time. Participants who report or demonstrate any distress during study assessments will be referred to counseling services at local agency with whom the PI has established linkages (The Center). All counseling resources are available to

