A power analysis was performed using the R package WebPower for a representative variable for each these three outcomes categories. Sample size can be derived based on effect size (f) and power (1- β). Here f= σ_m/σ , Cohen (1988, p. 275), σ_m is the standard deviation of population means and σ the standard deviation within the populations. Even though Cohen (1988) provides general magnitudes for small effect size: f = 0.1, medium effect size: f = 0.25, large effect size: f = 0.5, he argues that these guidelines are to be used when there is insufficient prior knowledge and "may not be reasonably descriptive in any specific area." The preliminary efficacy results derived from the proposed pilot trial will further inform our estimate of an effect size

of clinical interest for these outcomes. This information will be used to plan for a sufficiently powered confirmatory trial (e.g., R01).

1. Behavior Change Variable: use of self-protective behavior

Test procedure: paired two-sample t-test, one-sided, $\alpha = 0.05$, $s_d = 8$

Power calculation: GPower

	Power				
Effect Size (ES)	0.8	0.85	0.9	0.95	
1	398	462	550	694	
1.5	178	206	245	310	
2	101	117	139	175	
2.5	65	75	90	113	
3	46	53	63	79	

2. Attitudinal Mediator Variable: self-efficacy

Test procedure: paired two-sample t-test, one-sided, $\alpha = 0.05$, $s_d = 8$

Power calculation: GPower

	Power				
Effect Size (ES)	0.8	0.85	0.9	0.95	
1	398	462	550	694	
1.5	178	206	245	310	
2	101	117	139	175	
2.5	65	75	90	113	
3	46	53	63	79	

3. Reductions in Exposure to Victimization Variable: sexual victimization reduction

Test procedure: chi-square test for independence, two-sided, df = 2, α = 0.05

Power calculation: R package powerAnalysis

	Power				
Effect Size (ES)	0.8	0.85	0.9	0.95	
0.1	964	1093	1266	1545	
0.2	241	274	317	387	
0.3	108	122	141	172	
0.4	61	69	80	97	
0.5	39	44	51	62	

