Inferential analyses. We will use repeated measures one-way ANOVA to test if the tailored ESD curriculum has statistically significant effect on measures of behavioral and psychological/attitudinal change. If a significant effect is detected, we will use Tukey's pairwise-comparison procedure to compare all treatment means, with a 95% family confidence coefficient. To assess changes in exposure to victimization, we collapse into three levels: (a) no history of victimization; (b) moderate victimization; (c) severe victimization. For this categorical data, a chi-square test of independence will be performed to compare post-treatment vs. pre-treatment, 3-month FU vs. pre-treatment, and 6-month FU vs. pre-treatment respectively to assess the preliminary efficacy of the program, with a family-wise type I error controlled at 0.05 using Bonferroni procedure.

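### No look-back period is stated for victimization, and the immediate post-course contrast cannot be interpreted under most readings of its levels

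*SAP*

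**What the plan says.** The SAP, under Inferential analyses, states for victimization: "we collapse into three levels: (a) no history of victimization; (b) moderate victimization; (c) severe victimization". It then compares "post-treatment vs. pre-treatment, 3-month FU vs. pre-treatment, and 6-month FU vs. pre-treatment" by chi-square, "with a family-wise type I error controlled at 0.05 using Bonferroni procedure". The protocol (section 5, Research Design and Methodology) uses the same levels with one contrast fewer: "a chi-square test of independence will be performed to compare posttreatment vs. pre-treatment, and 6-month FU vs. pre-treatment".

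The protocol's survey schedule (section 6, Self-Report Questionnaires) is "baseline (before the ESD intervention), follow-up directly after the intervention, and 6-month follow-up". It contains no 3-month visit. The session dates in section 6 run from 7/11/21 to 8/8/21 (Series 1), 9/19/21 to 10/17/21 (Series 2) and 11/14/21 to 12/19/21 (Series 3).

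Neither document states the period over which victimization is recalled at any visit. The instruments are named, but they sit in an assessment packet that is not part of the documents.

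**The concern.** A category such as 'no victimization' has meaning only over a stated period. The SAP describes this outcome as a reduction in rates of exposure, yet names its lowest level in words that, read literally, describe a lifetime state. A lifetime state can only stay the same or worsen.

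The first follow-up adds a second difficulty. It closes a course of four to five weeks, so there is little new time at risk between baseline and that survey. Depending on the recall period, the contrast either counts largely the same events twice or compares a short period with a longer one.

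The estimate will be used. The protocol intends the exploratory results to shape the power analysis of the next RCT, and the SAP intends them to inform that trial's effect size. With no control group, nothing in this study would expose an artefact of the recall window. Replacing the chi-square test by a paired test would not remove it either.

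**Working it through.** **The plan's own figure.** The SAP's third power table assumes "chi-square test for independence, two-sided, df = 2, α = 0.05". With a noncentral chi-square on 2 df and noncentrality N·w², w = 0.5 and 80% power need N = 38.54, rounded up to 39, as tabulated. At w = 0.1 the result is 963.47, rounded up to 964. All 20 cells reproduce. The table is correct but does not say over what period w is measured.

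**Time between surveys.** First to last session is 28, 28 and 35 days. Protocol section 16 allows the surveys to be done on site around the first and last sessions, so the gap can be this short. It is longer if baseline was completed earlier.

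**Reading 1: lifetime at every visit.** Nobody can move to a better level. In simulation the test rejects in 0% of runs even if the course prevents every later event.

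**Reading 2: fixed 6-month recall at every visit**, baseline at session 1, 6 months = 182.6 days.
- Post-course overlap with baseline: (182.6 − 35)/182.6 = 81% to (182.6 − 28)/182.6 = 85%; in round months 5/6 = 83%.
- 3-month visit: about 4 months after baseline, overlap 2/6 = 33%.
- 6-month visit: about 7 months after baseline, no overlap.
- If 12-month prevalence is 30% (assumed), 6-month prevalence is 1 − 0.7^(6/12) = 16.3%. If the course stopped every event from its first day, the post-course figure would still be 1 − 0.7^(5/12) = 13.8%.

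With a 12-month recall the overlaps are 11/12 = 92% post-course and 5/12 = 42% at 6 months.

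**Reading 3: baseline window longer than the follow-up window** (for example, recall since the last survey). Assume a constant hazard and no course effect: λ = −ln(1 − p)/window.
- p = 30% over 6 months: λ = 0.3567/182.6 = 0.00195 per day. Over 28 days: 1 − exp(−0.0547) = 5.3%. Over 35 days: 1 − exp(−0.0684) = 6.6%. Apparent fall: 82% or 78%.
- p = 20% to 40% over 6 months gives 3.4% to 9.3%.
- If baseline was completed early enough to make the gap two months: 1 − 0.7^(2/6) = 11.2%, an apparent fall of 63%.
- p = 40% over 12 months against a 6-month follow-up: 1 − 0.6^(1/2) = 22.5%, an apparent fall of 44%.

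False rejection was simulated with 48 women per visit, 20,000 runs, equal rates of moderate and severe events, no course effect, and α = 0.05/2 = 0.025 (the protocol's two contrasts):

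| Baseline vs follow-up window | Prevalence, for 12-month rates of 20%, 30%, 50% | Rejection |
|---|---|---|
| 12 vs 1 month | 20→1.8%, 30→2.9%, 50→5.6% | 65%, 90%, >99% |
| 6 vs 1 month | 10.6→1.8%, 16.3→2.9%, 29.3→5.6% | 13%, 34%, 73% |
| 12 vs 6 months | 20→10.6%, 30→16.3%, 50→29.3% | 10%, 18%, 33% |
| 6 vs 6 months, no overlap | no change | 1.3%, 2.0%, 2.3% |

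Letting risk vary between women (gamma frailty) leaves the first row at 64% to >99% and lowers the third to 8% to 18%.

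**Reading 4: identical recall of about one month at every visit.** The windows are equal and essentially separate, so the contrast is fair, although the post-course window then covers the weeks of the course itself.

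**The case against.** A reader might infer that the plan compares unequal exposure windows at every visit and that all its victimization contrasts are therefore artefacts. The documents do not support that. They state no window, equal or unequal, and the recall periods may be fixed in the assessment packet. With a 6-month recall throughout, the 6-month contrast is like-for-like, and with a one-month recall so is the post-course one.

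Other points also count against a stronger claim:
- 'No history' may be only a loose label. The stated aim of reducing rates of exposure argues against a lifetime measure.
- The 28 and 35 days run between sessions. Baseline need only precede the course and may be completed at home, so the gap can be longer and both the overlap and the apparent fall smaller.
- All prevalences and baseline windows above are assumptions. That 12 versus 6 months gives a fall near the halving the protocol cites from an RCT follows from the windows chosen and says nothing about this study.
- The primary outcomes are recruitment and retention. Victimization is exploratory, and the SAP says the pilot is not powered for it.

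These points stand, and they limit the finding to an unspecified look-back and one contrast that fails under most readings. Lack of power does not dispose of it: low power excuses an imprecise estimate, whereas a window artefact biases it.

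**Conclusion.** The look-back is unspecified, level (a) is undefined, and the literal sense of its label conflicts with the aim of measuring a reduction. The post-course versus baseline contrast cannot measure a change in exposure under a lifetime, 6-month, 12-month or since-last-survey reading. It is fair only under an identical recall of about a month.

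Under the assumed rates, the error runs from no possible reduction (lifetime) to an apparent fall of about 80% with no course effect (6 months against 28 to 35 days), or 63% if the surveys were two months apart. The SAP's 3-month contrast is affected in part under a 6-month recall, and that visit is missing from the protocol's schedule. The 6-month contrast is sound if both windows are 6 months. The sizes rest on a constant hazard and assumed prevalences; the overlap rests on baseline being completed at about session 1.

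The matter should be corrected because the estimate is meant to feed the next trial's design. It does not touch the feasibility outcomes.

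**What to change.** In the SAP:
1. State the recall period used at each visit.
2. Remove the post-treatment victimization contrast from the tested family and report it descriptively at most. Do the same for the 3-month contrast if its window overlaps baseline, and reconcile that visit with the protocol's schedule.
3. Define levels (a) to (c) over one look-back of equal length, without overlap, at baseline and at 6 months, with (a) meaning none in that window.
4. Make 6 months versus baseline the tested contrast, reported as an estimate with an interval.
5. If the data collected used unequal windows, say so, do not read the contrast as a course effect, and do not use it for the RCT's effect size. Report rates per person-month only where event counts and window lengths are known; a three-level category alone does not supply counts.

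The cost is mainly SAP wording. The SAP is dated 1/18/2023 and the last planned session was 12/19/21, so on the planned schedule the 6-month surveys were already complete and the questionnaire could no longer be changed. The plan loses up to two of the SAP's three contrasts, or one of the protocol's two. A single tested contrast keeps the full 0.05, instead of 0.05/2 = 0.025 or 0.05/3 = 0.0167. Power stays low: with equal 6-month windows, 48 women and α = 0.025, a true halving (16% to 8.5%, or 29% to 16%) is detected in 8% to 18% of runs. It would be somewhat higher at 0.05.

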#### Describe the mechanisms in place to maintain confidentiality of participant data

Screening and survey responses as well as the internet-based consent form will be submitted to Qualtrics free of identifiable information. Electronic copies of those data will be stored on a secure password-protected online backed up lab server that is accessible only by lab personnel. If the participant completes consent orally, the oral consent form will also be stored on a secure password-protected online lab server free of identifiable information (containing participant ID only). Participant contact sheets will be stored separately from the study data, so that the study data will be collected using only a unique participant ID number, and are not identifiable by participant name. The self-assigned participant ID number will be used to link consents, questionnaire responses and interviews to one another. The Qualtrics anonymize responses feature will be used to ensure that IP addresses or other identifying information are not collected. Electronic copies of those data will be stored on a secure passwordprotected online backed up lab server in an encrypted and password protected data file (consistent with section 12 of CUNY Policy on Acceptable Use of Computer Resources) that is accessible only by lab personnel. Qualtrics' database does not hold sensitive or confidential response information after it is downloaded, however they do hold all survey responses in their data centers. The data centers utilize many security measures. Qualtrics' database access is restricted and requires authorization. All computer equipment (servers, SANs, switches, routers, etc.) is redundant and is located in secure, environmentally controlled data centers with 24/7 monitoring. Web traffic does not directly access the database and database requests are reversed proxy via an application server to the database. All information is secured via industry standard firewalls and stringent IT security policies and procedures. Qualtrics utilizes industry standard web application firewalls and DDOS protection. At no time will the downloaded or Qualtrics data be physically portable; the server system negates any need for USB drives or CDs for electronic data. A final copy of the downloaded data will be stored for a minimum of three years after the study is complete and closed out with IRB. If the participant makes the request to have a personal copy of the interview, we will store the audio and video recording file in Zoom for one week, during which the participant will have one week to download and store the file using a secure Zoom link to the recording, sent via email. At the end of the one week the video recording will be downloaded such that audio file and video file are downloaded as separate files; the video file will be deleted immediately and will never be saved or stored. The audio-only file will be saved for transcription and immediately uploaded to the secure password-protected online lab server. Audio files from the secure Zoom video interview will be uploaded to the secure password-protected online lab server. Only members of the research staff will be able to access the audio recordings taken during the lab session, and the participant if they request a personal copy. Participants will be informed that their responses will remain confidential, and that they have the right to erase the recording taken as part of this research. The audio recording will be stored electronically on a secure password-protected online lab server, labeled with the participant-generated ID number. The audio recordings will be used for verbatim (de-identified) audio transcription. Upon transcription, audio files will be stored for one additional week. This will allow an additional lab member to perform a quality-check on the transcription. Following quality assurance, the audio files will be destroyed. Personal identifier records will be kept in a secure online password-protected file on the secure password-protected online server, and any forms with identifying information will be stored separately from other study data. Personal identifier records will be kept in a secure online password-protected file on the secure password-protected online server, and any forms with identifying information will be stored separately from other study data. Records will be kept confidential to the level allowed by law and only the staff assigned to the study will have access to non-deidentified records. Information provided by study participants will not be released to outside sources. Data will not be stored or distributed for future studies. Regarding participants who agree to be contacted for future studies - we will store this contact information in a separate password protected file, on our secure online password-protected server. We will assign a new ID number to the current participant's study ID number. Participant's contact information will be stored with this new ID. The file that links participants' contact information and new ID will be stored in a separate password protected file, on the secure online password-protected lab server. The document that links both ID numbers will be password protected and stored in a separate password-protected file on the secure online password-protected lab server. If an individual requests their contact information be removed, we will remove their contact information from our database. Participant contact information will only be accessible to approved personnel.DSM Board Information Outlined in the NIH Grant: A DSMB is being created for this study by the study PI and NIH program officer. The PI has proposed

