Statistical Analysis Plan

"Empowerment Self-Defense Training for the Prevention of Victimization of Transgender Women" ID: R21MD014807 NCT04934189 1/18/2023

Statistical Design and Power

This R21 will use a non-experimental pilot study of 3 groups of 16 transgender women to assess preliminary feasibility and acceptability. A fully powered randomized controlled trial is neither practical nor advisable in this R21. The decision to use a single group, non-randomized design, rather than a randomized controlled trial (RCT), is best considered in light of critiques regarding the use of pilot RCTs to guide decision-making about whether to pursue larger-scale RCTs.⁷⁴⁻⁷⁶ The central point of these critiques is that because of their small size, pilot RCTs provide imprecise data on effect sizes, which can lead to both Type I and Type II errors. As a result, subsequent RCTs that are based on pilot RCTs may be underpowered (e.g., if pilot RCT suggests an artificially large effect size for the treatment [Type I error]) or not pursued (e.g., if pilot RCT suggests an artificially small effect size [Type II error]) even if the treatment could actually have been effective.⁷⁵ On the other hand, pilot trials do provide valuable information on the feasibility of study procedures, including recruitment, retention, implementation of the intervention, and data management. As the key objectives of this R21 are to develop the ESD self-defense training tailored for TW (Aim 1) and to assess its preliminary feasibility and acceptability (Aim 2), we will maximize the amount of useful information that can be gained about study feasibility and treatment efficacy in order to guide a future RCT of the new tailored violence prevention curriculum.

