Data Management. Following the CONSORT statement,⁸² we will track how many participants: (a) are told about the study; (b) are screened for the study; (c) do and do not meet inclusion criteria; (d) are invited to participate; and (e) actually enroll. Pre-inclusion attrition rates may reveal potential enrollment bias. To explore how differential refusal may affect generalizability of findings, we will also record the reasons for exclusion from and refusal to participate in the study. As recommended by the IOM Report,⁸³ we will model the effects of dropout patterns as data not missing at random using Bayesian analysis utilizing a pattern-mixture modeling approach. We will consider scale transformations, such as log, to decrease the effect of outliers.

Feasibility Analyses. The primary target outcomes of Aim 2 will be completion of the pilot study at the target recruitment total (n = 48), with < 25% dropout from assessments (Table 1. Research Plan). Secondary target outcomes related to assessment procedures, acceptability of the intervention, and laboratory and data management are detailed in Table 1 of the Research Plan. Successful completion of the pilot trial, including meeting or exceeding these benchmarks for success, will support the feasibility and acceptability of recruiting participants into a future RCT of the tailored ESD intervention using similar procedures and a similar population.

Power Analyses. Preliminary efficacy of the tailored ESD violence prevention intervention will be evaluated as an exploratory aim via administration of the battery of validated questionnaires assessing 1) behavior change variables (i.e., use of resistance tactics, self-protective behavior, and assertive relational communication); 2) psychological variables hypothesized to mediate the effects of the intervention on behavior (i.e., resistance self-efficacy, attributions of self-blame, rape myth acceptance, gender minority risk and resilience factors); and 3) reductions in rates of exposure to victimization) at baseline, post-intervention, and at the 3- and 6-month follow-up assessments.

Given its modest size and aims, this pilot is not powered to detect reductions in victimization exposure. Nonetheless, we will conduct exploratory analyses to evaluate potential trends that may emerge for the effects of treatment on behavior change, violence risk and resilience variables, and victimization.

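### Change in three-level victimization is tested as if the pre- and post-course answers came from different women, which makes the test conservative and costs power when answers within a woman are positively correlated

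*SAP*

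**What the plan says.** The SAP collapses victimization into three levels (none, moderate, severe). Under Inferential analyses it states that "a chi-square test of independence will be performed to compare post-treatment vs. pre-treatment, 3-month FU vs. pre-treatment", adds 6 months against pre-treatment, and plans this "with a family-wise type I error controlled at 0.05 using Bonferroni procedure". Protocol section 5 (Research Design and Methodology) names the same test for two contrasts: "a chi-square test of independence will be performed to compare posttreatment vs. pre-treatment, and 6-month FU vs. pre-treatment respectively".

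Power table 3 in the SAP is headed "Test procedure: chi-square test for independence, two-sided, df = 2, α = 0.05".

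Three statements show that the data are paired:
- SAP, Statistical Design and Power: "The decision to use a single group, non-randomized design".
- Protocol section 6: "Self-report questionnaires will be administered to each participant 3 times".
- Protocol section 16: "The self-assigned participant ID number will be used to link consents, questionnaire responses and interviews to one another".

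The SAP treats its other outcomes as within-person data, with repeated measures ANOVA in the analysis and paired t-tests in the power section. Neither document names a paired method for categorical data.

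**The concern.** Each contrast sets a follow-up wave against baseline in the same women. The chi-square test of independence takes the two waves as unrelated samples, so it uses the wrong variance for the change. If a woman's answers at two waves are positively correlated, that variance is too large. The test then rejects too rarely when nothing has changed, and it has less power when something has.

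The error therefore does not create false efficacy claims. The risk is that a real decline is read as no trend. The SAP's own case against pilot RCTs is that imprecise pilot results can lead to an effective treatment not being pursued. A test that discards the pairing adds to that risk.

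Table 3 carries the same assumption. It does not say whether its entries are women or observations, gives no within-person correlation, and uses alpha 0.05 although the analysis plans Bonferroni control.

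**Working it through.** **Inputs from the documents.** Three levels; 48 women; dropout below 25%, so about 0.75 × 48 = 36 women at the limit; df = 2 and alpha 0.05 in table 3. Bonferroni alpha is 0.05/3 = 0.0167 for the SAP's three contrasts and 0.05/2 = 0.025 for the protocol's two.

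**Step 1: reproduce table 3.** For an independence test, N solves P(χ²(df = 2, noncentrality N·w²) > critical value) = power. At alpha 0.05 the critical value is 5.991, and 80% power needs noncentrality 9.635, so N = 9.635/w². For w = 0.1, 0.2, 0.3, 0.4 and 0.5 this gives 964, 241, 108, 61 and 39, the SAP's column. All 20 cells reproduce. With df = 4 they do not (47.7 instead of 39 at w = 0.5). The table therefore counts independent observations in a 2 (wave) × 3 (level) layout.

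**Step 2: apply the planned Bonferroni level.** At 0.0167 the critical value is 8.189 and the noncentrality for 80% power is 12.558. The column becomes 1256, 314, 140, 79 and 51 independent observations.

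**Step 3: why pairing matters.** Let r_i and c_i be the counts at level i before and after, and n_ij the paired counts. With equal numbers at both waves, the planned statistic reduces to Σ(r_i − c_i)²/(r_i + c_i). Stuart-Maxwell uses d′V⁻¹d, where d holds two of the differences r_i − c_i, V_ii = r_i + c_i − 2n_ii and V_ij = −(n_ij + n_ji). Women who stay at the same level drop out of V. The planned test keeps them as if they were noise.

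**Step 4: size of the effect.** Assumptions, not in the documents: a latent bivariate normal cut at 40/35/25%; correlation 0.3, 0.5 or 0.7; and, for power, a latent shift of 0.4, which gives 55.8/30.0/14.1%. There were 40,000 simulated trials per setting.

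| Correlation | Rejection with no change, nominal 5%, n = 48 (planned) | Power at 0.0167, n = 48 (planned / Stuart-Maxwell) | Power at 0.0167, n = 36 (planned / Stuart-Maxwell) |
|---|---|---|---|
| 0.3 | 3.1% | 15% / 20% | 9% / 13% |
| 0.5 | 2.3% | 12% / 26% | 7% / 16% |
| 0.7 | 1.2% | 8% / 39% | 5% / 23% |

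Stuart-Maxwell rejects in 4.5% to 4.7% of no-change trials at nominal 5%. At nominal 0.0167 the planned test rejects in 0.9%, 0.6% and 0.3%, against 1.2% to 1.4%. At correlation 0 the planned test holds 5.2%, so the shortfall comes from the pairing. At the protocol's alpha of 0.025, power with 48 women is 18%, 16% and 12% against 25%, 32% and 46%.

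**Step 5: a larger assumed shift.** For 40/30/30% to 65/20/15% (w about 0.25), 48 women and alpha 0.0167, power is 43%, 42% and 40% against 50%, 61% and 79%.

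**Step 6: table 3 in women.** The shift in step 4 has w = 0.1734. The independence formula at 0.0167 gives 12.558/0.1734² = 418 observations, or 418/2 = 209 women measured twice. Stuart-Maxwell reaches 81%, 81% and 84% simulated power with 165, 132 and 100 women at correlations 0.3, 0.5 and 0.7.

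**The case against.** The SAP says that "this pilot is not powered to detect reductions in victimization exposure" and looks only for trends. Feasibility is judged on recruitment and dropout, so no decision hangs on this test. That stands, and it limits the weight of the point. It does not make the named test suitable for the data.

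The harm to later planning should not be overstated. The SAP says the pilot's efficacy results, not table 3, will inform the confirmatory trial. The observed proportions do not depend on the test, and a two-arm RCT compares different people. What remains is that table 3 misdescribes this pilot's own contrast.

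The two faults in table 3 pull in opposite directions. For the step 4 shift, its present basis gives 9.635/0.1734² = 321 observations, or 161 women measured twice. The corrected figures are 165, 132 and 100. At correlation 0.3 the errors nearly cancel; at 0.5 and 0.7 the table overstates the need.

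The power figures depend on the assumptions. At correlation 0 nothing is lost, and at −0.4 the planned test is liberal (7.3% at nominal 5%). For a very large shift (40/35/25% to 84/13/3%), both tests exceed 95% or come close to it even with 36 women. An unpaired test could also use the baselines of women who drop out: with 48 at baseline and 36 at follow-up its power is 10.7%, 9.1% and 6.7%, still below Stuart-Maxwell's 13%, 16% and 23% with 36 pairs.

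Finally, the conservative direction assumes the 2×3 layout. The df = 2 supports it, but Inferential analyses does not state a layout. A 3×3 pre-by-post test of independence would test association, not change. With levels 40/30/30%, no change and 48 women, it rejects in 22% of trials at correlation 0.3 and 96% at 0.7. Neither reading tests change validly.

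**Conclusion.** The concern holds. The victimization contrasts are paired and the named test is not. This follows from the documents alone. In the 2×3 layout implied by df = 2, with positive within-person correlation, the test is conservative and loses power. Under the step 4 assumptions the loss is small at correlation 0.3 (15% against 20%) and large at 0.7 (8% against 39%). Power for that shift stays below 50% even with the right test; for the larger shift in step 5 the right test reaches 50% to 79%. Table 3 treats observations as independent and omits the planned Bonferroni adjustment. Because the outcome is exploratory and declared not powered, this should be fixed but does not threaten the study's feasibility aims.

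**What to change.** In the SAP (Inferential analyses) and Protocol section 5:

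- Replace the chi-square test of independence with the Stuart-Maxwell test of marginal homogeneity for each follow-up against pre-treatment. Use a within-person permutation p-value if the change cells are sparse. A cumulative-logit GEE or mixed model clustered on participant is an acceptable alternative.
- Report the within-person change with a confidence interval, for example the paired difference in the proportion with any victimization.
- Keep Bonferroni over the contrasts actually made. The SAP lists three and the protocol two, because only the SAP has a 3-month assessment. The two should be reconciled so that the divisor is fixed.
- Restate table 3 in numbers of women, for paired data, at the Bonferroni alpha and with the assumed within-person correlation stated.

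The cost is wording in two documents, one recalculated table and a different software call on responses already linked by ID. No participants, visits or questions are added.
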